#### **Data Safety and Monitoring Plan:**

As seen in previous literature, both the Cheilectomy and Cartiva hemiarthroplasty procedures are relatively low risk. Furthermore, both procedures are indicated for patients with Grade 2 Hallux Rigidus. In the study done by Baumhauer et al, 9% of patients in the Cartiva group required implant removal and revision to a MTP joint fusion. All cases were due to persistent pain following Cartiva implant, with no evidence of significant bone loss or implant wear. Additionally, all cases of revision were successfully revised to an arthrodesis without complication. Additionally, there is an estimated 8-10% revision rate following Cheilectomy, with revision to arthrodesis being the common procedure. For this study, the primary surgeons will use their clinical judgement to determine if a patient will require a revision procedure if they have persistent pain following their initial surgery.

[name], surgical resident in the Department of Orthopedic Surgery will be responsible for the monitoring of this data, under supervision from the PI, [name]. We plan to assess our data and do a primary study evaluation when our enrollment has reached 25% of our stated enrollment goal. Unanticipated problems, adverse events, protocol deviations and violations will be reported to the IRB within 14 days following.

If, at the point of initial evaluation (25% of targeted enrollment), there is a higher than expected complication rate in either treatment arm, the study will be postponed at that time for further evaluation and possible discontinuation.

In the case that our initial evaluation shows negative results and occurs prior to a continuing review, we will contact the IRB with the information and seek to reevaluate or possible discontinue the study. All study team members have completed relevant training materials, are well versed in maintaining clinical integrity and data validity, and will be formally instructed in the

proper application of this protocol. Data/images will be evaluated by the PI, [name], as well as [name] and [name], study team members. This data will be passed to [name], whereupon it will be stored securely as outlined in the Data and Record Keeping section of our protocol."

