#### **Specific Aims/Study Objectives:**

The major hypothesis of this study is that patient outcomes following Cartiva implantation will be non-inferior to those undergoing cheilectomy for patients with grade 2 hallux rigidus. Results will include the FAAM ADL and Sport Subscores, SF-36 scores, Visual analog pain scores and peak active dorsiflexion in the 2 patient populations. Additional results will include secondary

surgeries and adverse events. These will be evaluated pre-operatively and then post operatively at 2 weeks, 6 weeks, 3 months, 1 year and 2 year follow up. The 2 year follow up visit will be the primary end point of the study.

The primary objective of this study will be to evaluate the Cartiva procedure compared to the Cheilectomy with the above stated patient reported outcomes and physical exam measures. These two procedures are both indicated for the patient population selected in this study, however post-surgical results have never been compared to one another in current literature. The secondary objective will be to identify subsets of the study population which may be better suited for one of the two procedures. Through statistical analysis, we will attempt to identify patient variables that may impact the surgical response. This will allow surgeons to appropriately counsel their patients on which procedure they would benefit from.

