Once a patient has agreed to take part in the study and has signed the informed consent, we will obtain baseline information from their medical records. This information will include gender, age, body mass index (BMI), smoking status, and prior 1st MTP joint procedures. At the patient's initial consultation visit (screening visit), their hallux rigidus grade will be defined by one of the 3 fellowship trained foot and ankle orthopedic surgeons based on the grading system from Coughlin and Shurnas. Patients will then be block randomized, by Department of Orthopedics and Rehabilitation statistician, into either one of the two treatment groups. Blocks will be 4 or 6 subjects in size to ensure balance in the two treatment arms across the duration of the study. The standard of care surgical treatment options are either Cartiva hemiarthroplasty or cheilectomy, and are the same for this study. Typically, a surgeon would have an informed discussion with the patient, listing the risks and benefits of each procedure and allow the patient to determine which procedure they would like to pursue. However, for the purpose and specific aims of this study, patients will be randomized into one of the two treatment options. Brief descriptions of the procedures are provided below:

**Cartiva hemiarthroplasty:** The procedure starts with a small incision over the top of the 1st MTP joint. The joint is exposed. Bone spurs on the metatarsal and proximal phalanx are resected, leaving approximately 2 mm of surrounding bone on the metatarsal head. A guide pin is placed within the

metatarsal and a drill is then used to create a site for the implant. The implant is then placed using the implant introducer. The incision is then closed and a sterile dressing is placed.

Cheilectomy: A small incision is made over the top of the 1st MTP joint. The joint is exposed. Bone spurs on the metatarsal and proximal phalanx are resected. The top of the metatarsal head is then cut with a sagittal saw. Additional bone spurs are resected. The incision is closed and a sterile dressing is placed.

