### **Statistical Considerations:**

The primary hypothesis of the study is to show that long term (2 year) functional outcomes for those undergoing Cartiva are no worse than the long term functional outcomes for those undergoing Cheilectomy. The primary outcome is the FAAM – ADL subscore from baseline to 2 years post-surgery. The MCID of FAAM-ADL is 8 units and we assume the SD of the difference in FAAM – ADL from baseline to 2 years post-surgery is near 17 units. To have 80% power in a non-inferiority test under these assumptions, we would need to recruit 57 subjects per group. For those subjects that are lost-to-follow-up or have a subsequent surgery we will impute the missing 2 year follow-up value in two ways: 1) by LOCF (last observation carried forward) and 2) by mean 2 year follow-up value for those in the same surgical group. We will then examine results from both method as a sensitivity analysis of our imputation method. To further assist in ensuring enough patients in each group we will inflate our sample size to 60 per group for a total of 120 patients.

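### The only safety look with a postponement rule is triggered by 25% enrolment, requires no post-operative follow-up and has no specified repeat, so it probably precedes most revisions

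*Combined protocol and SAP*

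**What the plan says.** The Data Safety and Monitoring Plan schedules one evaluation: "We plan to assess our data and do a primary study evaluation when our enrollment has reached 25% of our stated enrollment goal". The goal is set under Statistical Considerations: "we will inflate our sample size to 60 per group for a total of 120 patients". The action is tied to that same evaluation: "If, at the point of initial evaluation (25% of targeted enrollment), there is a higher than expected complication rate in either treatment arm", then "the study will be postponed at that time for further evaluation and possible discontinuation". No minimum follow-up is attached and no later evaluation is described.

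The expected rates in that section are revision rates. For the implant, "9% of patients in the Cartiva group required implant removal and revision to a MTP joint fusion", and "All cases were due to persistent pain following Cartiva implant". For cheilectomy the section gives 8-10%. Neither figure carries a time horizon there.

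Under Research Designs and Methods, patients enrol at the initial consultation and are operated on afterwards, with visits at 2 weeks, 6 weeks, 3 months, 1 year and 2 years. Under Specific Aims, "The 2 year follow up visit will be the primary end point of the study".

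Other oversight exists. Adverse events are assessed at each follow-up visit and reported to the IRB within 14 days. Continuing review is mentioned, and the investigators evaluate data and images. The Data Collection Form records loosening, osteolysis and indication for revision after surgery. Statistical Considerations plans secondary-surgery rates with 95% confidence intervals per group, as an analysis with no safety action attached.

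**The concern.** The trigger counts patients enrolled, not patients operated on or time since surgery. When the 30th patient joins, some of the 30 may still be awaiting surgery and the rest will have unequal follow-up, possibly short. The benchmarks are cumulative proportions revised, and the implant revisions are attributed to pain that persisted. A crude proportion from brief exposure set against such a benchmark will tend to look favourable whatever the true rate.

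At stake is how a quiet result is read. It could be taken as support for operating on the other 90 patients when it says little about revision. An excess emerging at 1 or 2 years would be visible case by case, but the plan states no by-arm comparison that would bring postponement into play. This is separate from the lack of a number for the expected rate. A numerical threshold applied once, this early, would have the same weakness.

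**Working it through.** **Size of the look.** The plan's 57 per group reproduces with margin 8, SD 17 and no true difference, using an exact t calculation at one-sided 5% (a level the plan does not state): power is 80.3%. Inflated to 60 per group, the total is 120, and 0.25 × 120 = 30. Allocation is to two arms ("Blocks will be 4 or 6 subjects in size to ensure balance in the two treatment arms across the duration of the study"), so about 15 per arm.

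**Count that exceeds the plan's figure.** 1/15 = 6.7%, below 9%. 2/15 = 13.3%, above 9%. Two revisions in an arm are the fewest that exceed 9%.

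**Assumptions not in the documents.** Total accrual T of 12, 24 or 48 months, evenly spread; 1 month from enrolment to surgery; constant revision hazard; the cited rates read as 2-year rates; a doubled rate of 18% as the excess worth finding.

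**Formulas.** The look falls at T/4. The i-th of 15 patients in an arm enters at e_i = (i − 0.5)/15 × T/4. Follow-up is f_i = max(T/4 − e_i − 1, 0) months. The hazard per month is h = −ln(1 − p)/24, which is 0.00393 for p = 0.09 and 0.00827 for p = 0.18. The chance that patient i has been revised is 1 − exp(−h f_i). The arm total is a sum of 15 independent events with these probabilities.

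**At the planned look, arm with true 2-year rate 18%:**

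| Total accrual | Look at month | Mean follow-up (months) | Expected revisions | P(1 or more) | P(2 or more) |
|---|---|---|---|---|---|
| 12 months | 3 | 0.7 | 0.08 | 8% | 0.3% |
| 24 months | 6 | 2.1 | 0.25 | 23% | 2.5% |
| 48 months | 12 | 5.0 | 0.61 | 46% | 12% |

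With full 2-year follow-up the same arm would expect 15 × 0.18 = 2.7 revisions.

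**Same 15 patients, all at 1 year.** The 1-year probability is 1 − (1 − p)^0.5: 4.6% for p = 0.09 and 9.4% for p = 0.18. From the binomial with n = 15:

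- True rate 18%: P(1 or more) = 77%, P(2 or more) = 42%.
- True rate 9%: P(1 or more) = 51%, P(2 or more) = 15%.

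**False alarms at 1 year with both arms at 9%.** One or more revisions in at least one arm: 1 − (1 − 0.507)² = 76%. Two or more in at least one arm: 1 − (1 − 0.150)² = 28%.

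**When the 1-year review would fall.** The last of the 30 reaches 1 year at T/4 + 1 + 12 months. For T = 12 that is month 16, after enrolment ends. For T = 24 it is month 19, with 19/24 = 79% enrolled. For T = 48 it is month 25, with 25/48 = 52% enrolled.

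**The case against.** The rule covers complications in general, not revision alone. Wound and early surgical problems can be seen from the 2-week visit, so an enrolment-triggered look has a legitimate purpose. Events are not hidden between looks, given the 14-day reporting and continuing review. All of this stands. None of it, however, carries a stated by-arm rate comparison or postponement rule for an excess that appears later.

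A reader might infer that revision cannot appear at this look, or that a clean result is close to certain. The documents do not support that. They give no accrual rate and no time-to-revision distribution, and no horizon for the 9% or 8-10%. The one dated figure, 5% at 5 years for the implant in Background and Significance, does not settle the timing. With 48 months' accrual, the model gives a 46% chance of at least one revision in a doubled-rate arm. Nor does the plan say that the look will never be repeated. Calling it an initial evaluation may imply others, but none is described.

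A later look is also no cure by itself. Seeing at least one revision at 1 year (77% at the doubled rate) is weak evidence of excess, because an arm at 9% shows one 51% of the time. Against the matching 1-year rate of 4.6%, one revision in 15 (6.7%) already counts as high. Repeating an undefined rule could therefore pause a sound trial. This objection stands and shapes the fix.

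**Conclusion.** The point holds in this form: the plan guarantees no post-operative follow-up at its only evaluation with a postponement rule, specifies no repeat, and gives only revision rates as benchmarks. The look is likely to come before most revisions for persistent pain can be observed, and it compares short, unequal exposure with cumulative rates.

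Under the stated assumptions, the chance that a doubled rate yields a count above 9% is 0.3% to 12% at the planned look. At 1 year it is 42%, with a 15% chance of the same count when nothing is wrong. The percentages depend on assumed accrual, surgical delay, horizon and hazard shape. If revisions cluster early the look sees more, and if they come late it sees less. The missing follow-up condition and the absence of a stated repeat are plain in the text and need no model. This is an inexpensive improvement that should be made; it does not invalidate the design.

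**What to change.** Keep the 25% look and say that it serves early complications. Add cumulative by-arm safety reviews of data already collected, for example when the first 30 operated patients reach 3 months and 1 year, at 50% and 75% enrolment, and at each IRB continuing review. The exact schedule is for the sponsor.

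Each review should show, per arm, patients operated on, person-months of follow-up, and complications and revisions with exact confidence intervals. These should be set against expected rates over matching follow-up, which means stating the horizon of each cited rate.

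State that postponement can be invoked at any of these reviews. The sponsor should set in advance a criterion that allows for small counts and repeated looks. A crude rate above the cited figure should lead to review, and a single event should not pause the trial by itself.

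The cost is protocol wording and repeat tabulation, with no extra visits or patients. The downside is false alarms: with both arms at 9%, the 76% and 28% figures above apply at the 1-year review alone, which is why the criterion matters. With fast accrual the 1-year review may come after most or all patients are enrolled. It would then protect few new patients but would still inform follow-up of those already operated on.

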Joint fusion has become common place in the treatment of advanced stage hallux rigidus, including grade 3 and 4. High fusion rates and patient satisfaction has been proven with fusion procedures in the first MTP joint. However, the loss of motion at the first MTP joint associated with the fusion procedure can interfere with activities such as running and jumping, and can make shoe wear choices difficult. These limitations led to the push for development of a joint replacement procedure, allowing for pain control and continued motion.

The use of silicone-based joint replacement has been met with mixed results, however concerns over the durability leading to implant fracture, osteolysis and difficulty of revision procedures has ultimately limited its use. Ceramic implants were found to have good short-term results, however concerns remain regarding the large amount of subsidence seen in follow up, as well as potential osteolysis. Furthermore, the amount of bone stock remaining following this procedure could make revision procedures quite challenging. Given these mixed results, there remained a significant drive to identify a joint replacement-type procedure with a device that could maintain adequate bone stock, preserve motion and withstand the daily stresses the first MTP joint faces.

This led to the use of the Cartiva implant, a polyvinyl alcohol hydrogel implant. Following extensive safety and wear testing, it was determined that this implant would be well suited for use in patients with hallux rigidus. Indicated for grade 2, 3 and 4 hallux rigidus, the initial study of Cartiva effectiveness compared outcomes of the implant versus arthrodesis. The prospective, randomized control trial evaluated 202 patients, with over 2/3 undergoing the Cartiva procedure. Both short and midterm outcomes were very promising. 5-year revision rates were found to be 5% with no evidence of implant loosening or surrounding bone complication. Additionally, the Cartiva implant was found to be equivalent to the gold standard, arthrodesis, when it came to post-operative patient outcome scores, range of motion and complications.

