With promising results from initial clinical trials, further evaluation into the efficacy and indications for Cartiva is necessary. To date, there is no published literature comparing Cheilectomy to Cartiva. Both procedures have shown to have beneficial results in patients with grade 2 hallux rigidus, yet these two procedures have not been directly compared in clinical trials since the invention of the Cartiva. With an estimated revision rate around 9% following Cheilectomy, it is possible that Cartiva could decrease the need for additional procedures.

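### Does the undefined expected complication rate at the 25% safety look need a numerical trigger?

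*Combined protocol and SAP*

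**What the plan says.** In the Data Safety and Monitoring Plan the team will "do a primary study evaluation when our enrollment has reached 25% of our stated enrollment goal". The rule at that look is that if "there is a higher than expected complication rate in either treatment arm, the study will be postponed at that time for further evaluation", with discontinuation as a possible outcome of the evaluation. A "surgical resident in the Department of Orthopedic Surgery will be responsible for the monitoring of this data", supervised by the principal investigator.

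The same section gives two reference figures shortly before the rule. For Cartiva, "9% of patients in the Cartiva group required implant removal and revision to a MTP joint fusion". For cheilectomy, "there is an estimated 8-10% revision rate following Cheilectomy". Both are revision rates. The section treats a complication as something distinct from a revision, since it reports that "all cases of revision were successfully revised to an arthrodesis without complication".

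The Background and Significance section has two further figures. For the implant, "5-year revision rates were found to be 5% with no evidence of implant loosening". For the comparator, "With an estimated revision rate around 9% following Cheilectomy, it is possible that Cartiva could decrease the need for additional procedures". The two Cartiva figures carry different citations.

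The section also requires adverse events and unanticipated problems to reach the IRB within 14 days, and it sends unfavourable results of the initial evaluation to the IRB when they precede a continuing review.

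**The concern.** The wording makes a pause compulsory, but the quantity that triggers it is not defined. Four things are left open: the reference rate, the events that count, the denominator (enrolled or operated patients) and the allowance for short follow-up. Because the look is timed by enrolment, and patients enrol at consultation before surgery, the last two could matter.

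With about 15 patients per arm, a single event is where these choices bite. If one occurs, the study team would be settling what the rule means after seeing the counts by arm, and the section describes no independent monitor. The result could be an unnecessary pause or a missed one. Writing the trigger as a number of patients seems a cheap repair.

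**Working it through.** **Size of the look.** Statistical Considerations sets a target of 120, so the look falls at 0.25 × 120 = 30 enrolled, or 15 per arm. With blocks of 4 or 6 in a single list, the split at 30 is 14 to 16 per arm. One event is 1/15 = 6.67% (1/16 = 6.25% to 1/14 = 7.14%).

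**Reference rate.** The smallest count whose rate is strictly above the reference, at n = 15 (2/15 = 13.3%):

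| Reference | Where stated | Trigger count |
|---|---|---|
| 5% (Cartiva, 5 years) | Background | 1 |
| 9% (Cartiva) | Monitoring plan | 2 |
| 8%, 9%, 10% (cheilectomy) | Monitoring plan; 9% also in Background | 2 |

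Every rate in the section that contains the rule gives two, at 14, 15 or 16 per arm. Only the Background's 5% gives one, and only for Cartiva. For cheilectomy no stated rate changes the answer.

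**Denominator.** If only operated patients count, 1/12 = 8.33% exceeds 8% but not 9%, and 1/11 = 9.09% exceeds 9% but not 10%. So against 9% one event triggers once 11 or fewer in the arm have had surgery. The documents give no consultation-to-surgery interval, so how often this would arise is unknown.

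**Follow-up.** One event exceeds a 9% scaled to accrued risk while the accrued fraction is below 0.0667/0.09 = 0.741. The protocol mentions no such scaling. Suppose 15 per arm, a true 9% in both arms, and revision standing in for complication. The scaled and unscaled readings then disagree when the worse arm has exactly one event: P(X ≤ 1)² − P(X = 0)². With a quarter, a third or half of the risk accrued:

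- 0.9562² − 0.7108² = 0.409
- 0.9270² − 0.6333² = 0.458
- 0.8555² − 0.5012² = 0.481

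**5% against 9%.** The two Cartiva readings disagree when Cartiva has one event and cheilectomy at most one. If one accrual fraction is applied to a true 5% and a true 9%, this is 15% at a quarter and 23% at a half. But the 5% is a five-year figure and the 9% has no stated horizon. If 5% accrues linearly over 5 years and 9% over 2 years (an assumption):

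- 6 months: risks 0.5% and 2.25%; 0.0699 × 0.9562 = 0.067
- 12 months: risks 1.0% and 4.5%; 0.1303 × 0.8555 = 0.111

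**What a fixed count would buy.** Take two or more events in either arm, 15 per arm, true rate 9% × fraction accrued. With q = P(X ≥ 2) at that rate and d = P(X ≥ 2) at double it, the false-pause probability is 1 − (1 − q)². The probability of a pause when one arm is doubled is 1 − (1 − q)(1 − d).

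| Fraction accrued | q | d | False pause, either arm | Pause, one arm doubled |
|---|---|---|---|---|
| 1/4 | 0.044 | 0.145 | 9% | 18% |
| 1/3 | 0.073 | 0.226 | 14% | 28% |
| 1/2 | 0.145 | 0.397 | 27% | 48% |
| 3/4 | 0.269 | 0.621 | 47% | 72% |
| 1 | 0.397 | 0.781 | 64% | 87% |

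The last row cannot describe this look, because the newest enrollees have had no time after surgery. In every row the two right-hand columns are too close for the count to discriminate well.

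**The case for a change.** The strongest case for a change is that a compulsory rule should mean one thing before data are seen. The Cartiva example needs only the protocol's own numbers, since 6.7% lies between its 5% and its 9%. Even a reader who takes the 9% beside the rule must still decide which events, patients and follow-up count. Those deciding are the study team, who see the arm counts. A sentence or two would settle it without delaying the look.

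That the definition is unwritten stands. Three things weaken the step from there to an amendment.

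- The denominator and scaling alternatives are not in the protocol. The largest disagreement figures (41-48%) compare possible readings of its silence and rest on assumed accrual fractions.
- A count of revisions would narrow the rule. At present any excess of complications compels a pause. A revision-only count would leave infection or implant loosening, for example, to discretion. The data for the wider judgement are collected: adverse events are assessed at each follow-up visit and recorded on their own form, and the Data Collection Form has fields for loosening, osteolysis and indication for revision.
- The count of two is itself what unscaled 9% with all enrolled patients gives. It picks one of the readings said to be unsettled, and under the scaled reading the answer would be one.

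**Conclusion.** No change to the plan is needed. This is missing detail that a monitoring team can fill sensibly from the section itself: 9% and 8-10% are printed just ahead of the rule, and at 14 to 16 enrolled per arm they agree on two events. The 5% is a five-year figure from another cited study. The two Cartiva rates are not a contradiction, although saying which one is the reference would be tidy.

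The consequence is bounded. A wrong call at this look means an unneeded evaluation or a missed one. Reporting to the IRB within 14 days runs regardless, and the two-year FAAM-ADL non-inferiority comparison is unaffected. No direction of failure and no wrong trial result has been shown.

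Nor would a numerical trigger be a clear gain. With a quarter to half of the risk accrued, two or more in either arm pauses 9-27% of trials with no excess and 18-48% with one arm doubled. At 15 per arm, judgement over all adverse events is a fair alternative to a count. These figures assume equal arms, a 9% baseline, revision as a proxy for complication, and accrual fractions that the documents do not give. If the team clarifies anything, a working note made before arm data are seen, naming the reference rate, counted events, denominator and follow-up, would be enough.
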